Title: Imaging Extrastriatal Dopamine Release in Tobacco Smokers and Nonsmokers

NCT: *NCT02348385*

Principal Investigator: *[name]*

Latest Approval Date: 08/22/2017

1. **Statement of Purpose:** State the scientific aim(s) of the study, or the hypotheses to be tested.

Our goal is to examine sex differences in amphetamine-induced dopamine (DA) release in tobacco smokers and nonsmokers.

Specific Aim 1: To determine sex differences in amphetamine-induced dopamine release in healthy tobacco smokers and nonsmokers.

[¹¹C]FLB-457 has been used in several PET centers and has recently been approved for use at the Yale University PET Center (HIC#100900739, PI: [name]). We would like to determine whether there are sex differences in amphetamine induced DA release in healthy tobacco smokers and nonsmokers. Specifically, 40 healthy tobacco smokers and 40 healthy nonsmokers will have an magnetic resonance imaging (MRI) scan followed on another day by two [¹¹C]FLB scans (ideally, the two PET scans will be carried out in the same day). Up to 3 hours before the second PET scan, amphetamine (0.4mg/kg, PO) will be administered. Smokers may be asked to return for a second MRI scan 3-5 weeks after their PET scans. We hypothesize women will have greater amphetamine-induced DA release than men in extra-striatal brain regions.

2. **Background:** Describe the background information that led to the plan for this project. Provide references to support the expectation of obtaining useful scientific data.

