Structural and functional (resting state) magnetic resonance imaging (MRI) scans (3 T) will be collected in each subject to co-register PET and MRI for image analysis. An MRI will be acquired at the Yale University MRI Center. Subjects will be taken through a ferromagnetic metal detector before entering the scan room. MR images provide a matching anatomical atlas for creating individualized region-of-interest templates for each subject. Subjects may be asked to participate in up to two MR sessions (one MR prior to each PET scan date).

PET experiments

PET experiments will be conducted at the Yale University PET Center.

For Aims smokers and nonsmokers will have up to two [^{11}C]FLB457 scans (2/day when feasible). If technical difficulties arise the second PET scan will be rescheduled as soon as possible.

We may ask subjects to refrain from eating 4-6 hours prior to injection and remain fasting until the study is over. Subjects will also be asked to refrain from drinking caffeinated beverages that day. Smokers may also be asked to abstain from smoking cigarettes starting at 10 p.m. the night before their PET scans day. For all women, a urine pregnancy test will be performed at the beginning of the imaging day at the Yale PET Center.

The preparation of the subject may include the placement of up to two venous lines and an arterial line. The purpose of the arterial line is for blood sampling of [^{11}C]FLB-457 to measure arterial concentration. The purpose of the two venous lines is for the [^{11}C]FLB-457 injection and to measure amphetamine or nicotine levels, respectively.

The arterial line may be placed after infiltration of the skin with 1 to 2% lidocaine by an experienced physician. A study physician or nurse will be present in the PET suite while the arterial line is in place.

Partial immobilization of the head will be done using a felt chin strap. PET scans are acquired as subjects rest using the HR+ or HRRT scanner. A transmission scan is obtained immediately before or after each emission scan.

For the emission scans, 10 mCi or less of [^{11}C]FLB457 will be injected intravenously.

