Up to two injections of [^{11}C]FLB457 are administered to the subject for the emission scans. Following each injection, scan emission data will be acquired for up to 120 minutes. When possible both FLB scans will be performed on the same day, if the second scan is cancelled, e.g., the radiotracer synthesis fails, the second scan will be rescheduled as soon as possible on a different day, and the amphetamine or stress reactivity paradigm will be administered again, using the same protocol. For Aim 1, we will wait at least 4 days in order to allow the amphetamine to clear.

At -1, 5, 20, 40, and 60 minutes post visualization, plasma samples will be obtained. Plasma samples will be obtained to analyze for cortisol, ACTH, NE, EPI, and other stress related hormones. We will assess hypothalamic-pituitary-adrenal (HPA) axis function using samples of adrenocorticotrophin hormone (ACTH) and cortisol and plasma norepinephrine (NE) and epinephrine (EPI) during the stress behavior challenges.

Amphetamine administration (oral)

Dextroamphetamine sulfate is the dextro isomer of the compound d,l-amphetamine sulfate, a sympathomimetic amine of the amphetamine group. It is an FDA approved drug available for the treatment of narcolepsy and attention deficit hyperactivity disorder (maximum approved total daily dose of 5-60 mg). After the first scan, dextro-amphetamine (0.4 mg/kg, PO) will be given in increments of 5 mg, as it is available in 5 mg tablets, and will be rounded up to approximate 0.4 mg/kg total dose **without exceeding it**. The dextro-amphetamine will be given at 0.4mg/kg.

The total dextro-amphetamine dose will not exceed 40 mg per scan. A second transmission and emission scan will be acquired 3-hours post amphetamine identical to the methods outlined previously. The timing of the second [¹¹C]FLB 457 administration and subsequent PET scanning (i.e., 3 hours) corresponds to the time of maximum plasma concentration of amphetamine as stated in the respective FDA-approved product labeling. EKG and frequent BP monitoring may occur throughout the study and until the vital signs are within normal limits. Supplemental oxygen will be provided via nasal cannula if necessary. If the systolic BP reaches or exceeds 200 mmHg for more than 5 minutes, the study doctor will take the appropriate clinical measures in order to lower the BP, which may include phentolamine administration (5 mg IV over 10 min) or other appropriate measures.

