6. **Required HIPAA Authorization:** If the research involves the creation, use or disclosure of protected health information (PHI), separate subject authorization is required under the HIPAA Privacy Rule. Indicate which of the following forms are being provided:

- Compound Consent and Authorization form
- HIPAA Research Authorization Form

SECTION VI: PROTECTION OF RESEARCH SUBJECTS

1. **Risks:** Describe the reasonably foreseeable risks, including risks to subject privacy, discomforts, or inconveniences associated with subjects' participation in the research.

- a. Risks of [¹¹C]FLB457

The Yale-New Haven Hospital Radiation Safety Committee (RSC) will review the use of radiation in this research study, and no subjects will be enrolled until RSC approval is obtained. This research study involves exposure to radiation from [¹¹C]FLB457_PET scanning. This radiation exposure is not necessary for medical care and is for research purposes only. The total amount of radiation an individual subject will receive in this study is from **up to 4** injection(s) with a total of ≤ 10 mCi (per injection) from [¹¹C]FLB457, plus transmission scans of the brain.

Although each organ will receive a different dose, the maximum amount of radiation exposure subjects will receive from this study is equal to an effective dose of **1.24 rem** for a total of **up to 40 mCi** of [¹¹C]FLB457 in 4 injections (10 mCi per injection). That is, a total of **1.24 rem** for 4 scan(s) is the amount of radiation exposure that a subject will receive from the study. This calculated value is used to relate the dose received by each organ to a single value.

The amount of radiation subjects will receive in this study is below the dose guidelines established by the FDA and monitored by the Yale-New Haven Hospital Radiation Safety Committee for research subjects. This guideline sets an effective dose limit of 5 rem per year.

c. Risks of oral d-amphetamine

Risks of amphetamine administration include both medical and psychiatric risks.

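### Section VI counts four [11C]FLB457 injections and 40 mCi per subject; the rest of the protocol has two scans or injections, and its dosimetry text totals 20 mCi

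*Combined protocol and SAP*

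**What the plan says.** Section VI, 1. Risks, item a, allows up to 40 mCi of tracer "in 4 injections (10 mCi per injection". It then says that 1.24 rem "for 4 scan(s) is the amount of radiation exposure that a subject will receive from the study". The exposure is described as tracer "plus transmission scans of the brain", and is judged acceptable against a yearly guideline: "This guideline sets an effective dose limit of 5 rem per year".

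The other sections give two:

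- **Statement of Purpose** and **3.1 Overall Research Design**: two tracer scans per subject; "ideally, the two PET scans will be carried out in the same day".
- **PET experiments** (Research Plan): "For Aims smokers and nonsmokers will have up to two" tracer scans; "Up to two injections of" the tracer for the emission scans; each injection 10 mCi or less.
- **Identification of Drug, Device or Biologic**: two injections, each of at most 10 mCi.
- **Background Information, Radiation exposure**: two injections, with a whole-study total of no more than 20 mCi. The same text gives 20 mCi as the most that may be given in a single study, citing a 3 rem limit and 0.0739 rad per mCi to the ovaries.
- **Inclusion criteria**: two PET scans and one MRI.

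Only the Radiation exposure text states the 20 mCi total outright. The drug section implies it (2 × 10), and the remaining sections give counts of scans or injections.

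**The concern.** Section VI is where the protocol sets out the radiation a subject will receive, and its injection count and activity are double those in the procedures. The figure is used in two places. Under Minimizing Risks, item a, the radiation dose goes to the radiation safety committee for approval, and Section VI bars enrolment until that approval is obtained. The exclusion criteria and the same Minimizing Risks item also exclude candidates whose yearly research exposure would pass the limits, and Minimizing Risks counts this study's own dose in that total. The protocol supports two values for that term. The choice could matter for a candidate with substantial research exposure in the previous year, although nothing in the documents shows that such a candidate exists.

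If two injections is correct, Section VI overstates the exposure. If four is correct, the dosimetry text has assessed only half of it.

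**Working it through.** **Inputs**

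- Section VI, Risks, item a: 4 injections, 10 mCi each, 1.24 rem for 4 scans; 5 rem per year guideline.
- Drug section and Radiation exposure text: 2 injections of at most 10 mCi.
- Radiation exposure text: stated single-study maximum 20 mCi; limit 3 rem per study; ovaries 0.0739 rad per mCi; kidneys 0.0273 rad per mCi; yearly limits 5 rad (gonads) and 15 rad (other organs).
- Assumption: 1 rad = 1 rem.

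**Step 1. Total activity (injections × mCi per injection)**

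- Section VI: 4 × 10 = 40 mCi, which reproduces its figure.
- Drug section and Radiation exposure text: 2 × 10 = 20 mCi, which reproduces the whole-study total.
- Ratio: 40 / 20 = 2.0. Section VI's total is therefore also twice the stated single-study maximum.

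**Step 2. Can the procedures yield more than two injections?**

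The rescheduling rule in PET experiments moves a cancelled second scan to another day and repeats the challenge. It adds no third or fourth tracer injection. Payments for Participation mentions an Aim 3 that the protocol does not otherwise describe, and nothing links it to extra injections.

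**Step 3. Does the stated maximum follow from its inputs?**

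Maximum activity = dose limit / dose per mCi = 3 / 0.0739 = 40.6 mCi, against 20 mCi as stated. The text refers to a dose table that is not in the available copy and may explain the difference.

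**Step 4. Tracer organ dose (activity × coefficient)**

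| | 20 mCi | 40 mCi |
|---|---|---|
| Ovaries | 20 × 0.0739 = 1.478 rad | 40 × 0.0739 = 2.956 rad |
| Share of 3 rem per study | 49.3% | 98.5% |
| Margin to 3 rem | 1.522 | 0.044 |
| Share of 5 rad per year | 29.6% | 59.1% |
| Kidneys (15 rad per year) | 20 × 0.0273 = 0.546 rad | 40 × 0.0273 = 1.092 rad |

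No stated organ limit is exceeded by the tracer in either column. The available copy gives no transmission-scan dose.

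**Step 5. Effective dose**

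- Per scan: 1.24 / 4 = 0.31 rem.
- Two scans: 2 × 0.31 = 0.62 rem, assuming each scan contributes equally.
- Against 5 rem per year: 1.24 / 5 = 24.8%; 0.62 / 5 = 12.4%.

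PET experiments says "A transmission scan is obtained immediately before or after each emission scan", so halving the scans also halves the transmission scans. The scaling therefore holds whether or not 1.24 rem includes them; if it does not, their dose is additional.

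**The case against.** The best defence is that the four injections are left over from a larger, multi-aim protocol. PET experiments mentions a stress paradigm, and the payment section mentions Aim 3. On that reading the error is clerical and errs on the safe side: the operative sections cap injections at two, so Section VI would overstate exposure and could only exclude too many candidates. The committee's separate approval is a further control. The comparison with the 20 mCi maximum is also weak, because that maximum does not follow from its own inputs.

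Much of this is fair. Carry-over is plausible, although no section says so. Twice the stated maximum must not be read as a breached organ limit, since 2.96 rad is below 3 rem. The committee filings are not available, so it is not shown that the committee received conflicting totals.

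The defence does not remove the contradiction. Carried-over text would itself need correcting. Section VI cannot be read as a harmless upper bound, because it also presents the four-scan dose as what the subject will receive, and its total exceeds the ceiling the protocol states for itself. The safe-side argument assumes that two is the right count, which the documents do not establish.

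**Conclusion.** The concern holds. The protocol contradicts itself on radiation per subject: 4 versus 2 injections and 40 versus 20 mCi, a factor of two. Effective dose is 1.24 rem as stated for four scans, or 0.62 rem for two if scans contribute equally. The tracer dose to the ovaries would be 2.96 or 1.48 rad from the protocol's coefficient, taking 1 rad = 1 rem.

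A second, lesser inconsistency is the single-study maximum: 20 mCi as stated against 40.6 mCi from the inputs beside it, subject to the dose table that could not be seen.

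No organ or yearly limit is shown to be exceeded by the tracer, and no affected candidate is shown. It should still be corrected, because this is a per-subject safety figure used for committee approval and for an exclusion criterion. Confidence in the contradiction is high. Its practical consequences depend on filings and candidates that the documents do not show.

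**What to change.** Reconcile the Statement of Purpose, 3.1, PET experiments, the drug section, the Radiation exposure text and Section VI on four items: number of injections, total activity, effective dose, and the derivation of the single-study maximum. Then recompute organ and effective dose for the injections that subjects in this protocol can actually receive, and state whether transmission scans are included. Use that single figure in the risk statement and in the cumulative-exposure check under the exclusion criteria and Minimizing Risks. If an undescribed aim accounts for the extra injections, describe it; otherwise remove the leftover references. Which count is right is for the investigators to establish.

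The cost is corrected text in the drug section and Section VI, a check against the dose table that the Radiation exposure text cites, and notice to the IRB and the radiation committee. Endpoint, analysis and sample size do not change.
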